7.4.6 Baseline Exams

- Baseline signs and symptoms (**Table 14**)
- Baseline hematology: WBC, neutrophils, platelets, hemoglobin, RBC, lymphocytes, monocytes, eosinophils, basophils (**Table 15**)
- Baseline serum chemistry: Total bilirubin, AST, ALT, alkaline phosphatase, LDH, serum creatinine, chloride, sodium, albumin, potassium, calcium, magnesium, ALP, glucose, amylase, lipase, CEA (**Table 16**)
- Baseline Thyroid Function Tests (**Table 17**)
- Baseline Coagulation Tests (**Table 18**)
- Baseline ECG (**Table 19**)
- Baseline urinalysis (**Table 20**)

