7.7 Safety

The safety analyses will be based on the All Treated population defined in Section 6. Adverse events and laboratories are graded and categorized using the CTCAE v4.0 criteria except where CTCAE grades are not available.

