7.7.2 Laboratory Evaluations

For patients on Durva+Treme, laboratory evaluations reported on Treatment Report or 4-Week Post-Treatment Follow-Up Report for patients on the Durva+Treme arm will be included in the calculation for laboratory adverse events on Durva+Treme. All laboratory evaluations reported after baseline assessment will be included in the calculation for overall laboratory adverse events. Laboratory results will be classified according to CTCAE version 4.0. Laboratory tests that are not covered by the CTCAE grading system will be summarized according to the following categories: normal and above the upper normal limits.

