7.6.2.3 Thyroid Function Tests

- TSH, T3 free, T3 total, T4 free, T4 total on Durva+Treme (**Table 51**)
- Overall TSH, T3 free, T3 total, T4 free, T4 total (**Table 52**)

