	DURVA+TREME			BSC		
	N=***			N=***		
	Worse Grade					
	Grade 3	Grade 4	Grade 5	Grade 3	Grade 4	Grade 5
Patients with any severe AE	** (**)	** (**)	** (**)	** (**)	** (**)	** (**)
Patients with severe AE within category:						
Category 1 ⁽¹⁾						
Event 1	** (**)	** (**)	** (**)	** (**)	** (**)	** (**)
Event 2	** (**)	** (**)	** (**)	** (**)	** (**)	** (**)
Event 3	** (**)	** (**)	** (**)	** (**)	** (**)	** (**)
...						
Category 2 ⁽¹⁾						
Event 1	** (**)	** (**)	** (**)	** (**)	** (**)	** (**)
...						

(1) Patients may have more than one event within a category.

Table 47: Hematology during Durvalumab and Tremelimumab Treatment

Data set: All Treated Patients on DURVA+TREME Arm	
	Number of Patients (%)
	DURVA+TREME N = ***
Hemoglobin	
Grade 1	** (**)
Grade 2	** (**)
Grade 3	** (**)
Grade 4	** (**)
Platelet	
Grade 1	** (**)
Grade 2	** (**)
Grade 3	** (**)
Grade 4	** (**)
WBC	
Grade 1	** (**)
Grade 2	** (**)
Grade 3	** (**)
Grade 4	** (**)
Neutrophils	
Grade 1	** (**)
Grade 2	** (**)
Grade 3	** (**)
Grade 4	** (**)
RBC	
Normal	** (**)
High ⁽¹⁾	** (**)
Lymphocytes	
Grade 1	** (**)
Grade 2	** (**)
Grade 3	** (**)
Grade 4	** (**)
Monocytes	
Normal	** (**)
High ⁽¹⁾	** (**)
Eosinophils	
Normal	** (**)
High ⁽¹⁾	** (**)
Basophils	
Normal	** (**)
High ⁽¹⁾	** (**)

⁽¹⁾ Greater than upper normal limit

Table 48: Overall Hematology: Worst Grade per Patient

Data set: All Treated Patients		
	Number of Patients (%)	
	DURVA+TREME N = ***	BSC N = ***
Hemoglobin		
Grade 1	** (**)	** (**)
Grade 2	** (**)	** (**)
Grade 3	** (**)	** (**)
Grade 4	** (**)	** (**)
Platelet		
Grade 1	** (**)	** (**)
Grade 2	** (**)	** (**)
Grade 3	** (**)	** (**)
Grade 4	** (**)	** (**)
WBC		
Grade 1	** (**)	** (**)
Grade 2	** (**)	** (**)
Grade 3	** (**)	** (**)
Grade 4	** (**)	** (**)
Neutrophils		
Grade 1	** (**)	** (**)
Grade 2	** (**)	** (**)
Grade 3	** (**)	** (**)
Grade 4	** (**)	** (**)
RBC		
Normal	** (**)	** (**)
High ⁽¹⁾	** (**)	** (**)
Lymphocytes		
Grade 1	** (**)	** (**)
Grade 2	** (**)	** (**)
Grade 3	** (**)	** (**)
Grade 4	** (**)	** (**)
Monocytes		
Normal	** (**)	** (**)
High ⁽¹⁾	** (**)	** (**)
Eosinophils		
Normal	** (**)	** (**)
High ⁽¹⁾	** (**)	** (**)
Basophils		
Normal	** (**)	** (**)
High ⁽¹⁾	** (**)	** (**)

⁽¹⁾ Greater than upper normal limit

**Table 49: Serum Chemistry during Durvalumab and Tremelimumab
Treatment: Worst Grade per Patient**

Data set: All Treated Patients on DURVA+TREME Arm	
	Number of Patients (%)
	DURVA+TREME N = ***
Total bilirubin	

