Grade 1	** (**)
Grade 2	** (**)
Grade 3	** (**)
Grade 4	** (**)
Alkaline phosphatase	
Grade 1	** (**)
Grade 2	** (**)
Grade 3	** (**)
Grade 4	** (**)
ALT	
Grade 1	** (**)
Grade 2	** (**)
Grade 3	** (**)
Grade 4	** (**)
AST	
Grade 1	** (**)
Grade 2	** (**)
Grade 3	** (**)
Grade 4	** (**)
LDH	
Normal	** (**)
High ⁽¹⁾	** (**)
Serum Creatinine	
Grade 1	** (**)
Grade 2	** (**)
Grade 3	** (**)
Grade 4	** (**)
Hypernatremia	
Grade 1	** (**)
Grade 2	** (**)
Grade 3	** (**)
Grade 4	** (**)
Hyponatremia	** (**)
Grade 1	** (**)
Grade 2	** (**)
Grade 3	** (**)
Grade 4	** (**)
Hyperkalemia	
Grade 1	** (**)
Grade 2	** (**)
Grade 3	** (**)
Grade 4	** (**)
Hypokalemia	
Grade 1	** (**)
Grade 2	** (**)
Grade 3	** (**)

Grade 4	** (**)
Hypercalcemia	
Grade 1	** (**)
Grade 2	** (**)
Grade 3	** (**)
Grade 4	** (**)
Hypocalcemia	
Grade 1	** (**)
Grade 2	** (**)
Grade 3	** (**)
Grade 4	** (**)
Hypermagnesemia	
Grade 1	** (**)
Grade 2	** (**)
Grade 3	** (**)
Grade 4	** (**)
Hypomagnesemia	
Grade 1	** (**)
Grade 2	** (**)
Grade 3	** (**)
Grade 4	** (**)
Hyperalbuminemia	
Grade 1	** (**)
Grade 2	** (**)
Grade 3	** (**)
Grade 4	** (**)
Hypoalbuminemia	
Grade 1	** (**)
Grade 2	** (**)
Grade 3	** (**)
Grade 4	** (**)
Chloride	
Normal	** (**)
High ⁽¹⁾	** (**)
ALP	
Grade 1	** (**)
Grade 2	** (**)
Grade 3	** (**)
Grade 4	** (**)
Amylase	
Grade 1	** (**)
Grade 2	** (**)
Grade 3	** (**)
Grade 4	** (**)
Lipase	
Grade 1	** (**)
Grade 2	** (**)
Grade 3	** (**)
Grade 4	** (**)
CEA	
Normal	** (**)
High ⁽¹⁾	** (**)

⁽¹⁾ Greater than upper normal limit

Table 50: Overall Serum Chemistry: Worst Grade per Patient

Data set: All Treated Patients		
	Number of Patients (%)	
	DURVA+TREME N = ***	BSC N = ***
Total bilirubin		
Grade 1	** (**)	** (**)
Grade 2	** (**)	** (**)
Grade 3	** (**)	** (**)
Grade 4	** (**)	** (**)
Alkaline phosphatase		
Grade 1	** (**)	** (**)
Grade 2	** (**)	** (**)
Grade 3	** (**)	** (**)
Grade 4	** (**)	** (**)
ALT		
Grade 1	** (**)	** (**)
Grade 2	** (**)	** (**)
Grade 3	** (**)	** (**)
Grade 4	** (**)	** (**)
AST		
Grade 1	** (**)	** (**)
Grade 2	** (**)	** (**)
Grade 3	** (**)	** (**)
Grade 4	** (**)	** (**)
LDH		
Normal	** (**)	** (**)
High ⁽¹⁾	** (**)	** (**)
Serum Creatinine		
Grade 1	** (**)	** (**)
Grade 2	** (**)	** (**)
Grade 3	** (**)	** (**)
Grade 4	** (**)	** (**)
Hypernatremia		
Grade 1	** (**)	** (**)
Grade 2	** (**)	** (**)
Grade 3	** (**)	** (**)
Grade 4	** (**)	** (**)
Hyponatremia		
Grade 1	** (**)	** (**)
Grade 2	** (**)	** (**)
Grade 3	** (**)	** (**)

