Grade 4	** (**)	** (**)
Hyperkalemia		
Grade 1	** (**)	** (**)
Grade 2	** (**)	** (**)
Grade 3	** (**)	** (**)
Grade 4	** (**)	** (**)
Hypokalemia		
Grade 1	** (**)	** (**)
Grade 2	** (**)	** (**)
Grade 3	** (**)	** (**)
Grade 4	** (**)	** (**)

Hypercalcemia		
Grade 1	** (**)	** (**)
Grade 2	** (**)	** (**)
Grade 3	** (**)	** (**)
Grade 4	** (**)	** (**)
Hypocalcemia		
Grade 1	** (**)	** (**)
Grade 2	** (**)	** (**)
Grade 3	** (**)	** (**)
Grade 4	** (**)	** (**)
Hypermagnesemia		
Grade 1	** (**)	** (**)
Grade 2	** (**)	** (**)
Grade 3	** (**)	** (**)
Grade 4	** (**)	** (**)
Hypomagnesemia		
Grade 1	** (**)	** (**)
Grade 2	** (**)	** (**)
Grade 3	** (**)	** (**)
Grade 4	** (**)	** (**)
Hyperalbuminemia		
Grade 1	** (**)	** (**)
Grade 2	** (**)	** (**)
Grade 3	** (**)	** (**)
Grade 4	** (**)	** (**)
Hypoalbuminemia		
Grade 1	** (**)	** (**)
Grade 2	** (**)	** (**)
Grade 3	** (**)	** (**)
Grade 4	** (**)	** (**)
Chloride		
Normal	** (**)	** (**)
High ⁽¹⁾	** (**)	** (**)
Amylase		
Grade 1	** (**)	** (**)
Grade 2	** (**)	** (**)
Grade 3	** (**)	** (**)
Grade 4	** (**)	** (**)
Lipase		
Grade 1	** (**)	** (**)
Grade 2	** (**)	** (**)
Grade 3	** (**)	** (**)
Grade 4	** (**)	** (**)
CEA		
Normal	** (**)	** (**)
High ⁽¹⁾	** (**)	** (**)

⁽¹⁾ Greater than upper normal limit

Table 51: Thyroid Function Tests: Worst during Durvalumab and Tremelimumab Treatment

Data set: All Treated Patients on DURVA+TREME Arm	
	Number of Patients (%)
	DURVA+TREME N = ***
TSH	
Normal	** (**)
<1-0.5xLLN	** (**)
<0.5-0.1xLLN	** (**)
<0.1xLLN	
T3 Free	** (**)
Normal	** (**)
<1-0.5xLLN	** (**)
<0.5-0.1xLLN	** (**)
<0.1xLLN	** (**)
T3 Total	
Normal	** (**)
<1-0.5xLLN	** (**)
<0.5-0.1xLLN	** (**)
<0.1xLLN	** (**)
T4 Free	
Normal	** (**)
<1-0.5xLLN	** (**)
<0.5-0.1xLLN	** (**)
<0.1xLLN	** (**)
T4 Total	
Normal	** (**)
<1-0.5xLLN	** (**)
<0.5-0.1xLLN	** (**)
<0.1xLLN	** (**)

Table 52: Thyroid Function Tests: Worst during Study

Data set: All Treated Patients		
	Number of Patients (%)	
	DURVA+TREME N = ***	BSC N = ***
TSH		
Normal	** (**)	** (**)
<1-0.5xLLN	** (**)	** (**)
<0.5-0.1xLLN	** (**)	** (**)
<0.1xLLN	** (**)	** (**)
T3 Free		
Normal	** (**)	** (**)
<1-0.5xLLN	** (**)	** (**)
<0.5-0.1xLLN	** (**)	** (**)
<0.1xLLN	** (**)	** (**)
T3 Total		
Normal	** (**)	** (**)
<1-0.5xLLN	** (**)	** (**)
<0.5-0.1xLLN	** (**)	** (**)

T4 Free	<0.1xLLN	** (**)	** (**)
	Normal	** (**)	** (**)
	<1-0.5xLLN	** (**)	** (**)
	<0.5-0.1xLLN	** (**)	** (**)
	<0.1xLLN	** (**)	** (**)
T4 Total			

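### SAP Tables 17, 51 and 52 have no row for a raised TSH, T3 or T4, and the two post-baseline shells match neither display that SAP 7.7.2 allows

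*SAP*

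**What the plan says.** SAP 7.7 has laboratory results "graded and categorized using the CTCAE v4.0 criteria except where CTCAE grades are not available". SAP 7.7.2 adds that tests outside the CTCAE system "will be summarized according to the following categories: normal and above the upper normal limits". It also sets two reporting windows. On-treatment results come from the Treatment Report and the 4-Week Post-Treatment Follow-Up Report. For the whole study, "All laboratory evaluations reported after baseline assessment will be included in the calculation for overall laboratory adverse events".

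SAP 7.6.2.3 (Thyroid Function Tests) lists "TSH, T3 free, T3 total, T4 free, T4 total on Durva+Treme" for Table 51, titled "Thyroid Function Tests: Worst during Durvalumab and Tremelimumab Treatment", and the same five tests overall for Table 52. It names no categories. SAP 7.4.6 lists "Baseline Thyroid Function Tests" for Table 17, also without categories.

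The categories appear only in the Appendix 1 shells. In Tables 17, 51 and 52 every thyroid test has the same four rows: Normal, and three bands below LLN cut at 0.5 and 0.1 times LLN.

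**The concern.** Laboratory parameters are a stated safety endpoint (SAP 4.3), and the protocol lists both hyper- and hypothyroidism as adverse events of special interest (9.1.1). TSH is in the scheduled biochemistry panel of both arms, and T3 and T4 must be measured when it is abnormal (protocol 5.1 and 5.2). The data are therefore collected, but the planned tables have nowhere to put a value above ULN.

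A programmer working from the shells has two options for such a value: leave it out, or let it fall into Normal. The second would make thyroid function look better than it was. Because Table 17 has the same gap, a reader also could not see from the tables whether an elevation was already present at baseline.

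**Working it through.** No formula is involved. The check is a row count and a comparison of shells with text.

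**Rows in the thyroid shells**
- Tables 51 and 52: 5 tests x 4 rows x 2 tables = 40 rows. Normal: 5 x 2 = 10. Below LLN: 5 x 3 x 2 = 30. Above ULN: 40 - 10 - 30 = 0.
- Table 17: 5 x 4 = 20 rows. Normal: 5. Below LLN: 15. Above ULN: 0.

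The same four labels recur in all 15 test blocks (5 tests x 3 tables), so text lost in reading the PDF does not explain the gap.

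**Comparison with the two displays in SAP 7.7.2**
- If the thyroid tests are treated as graded, Grade rows are expected. There are none, whereas the coagulation shells (Tables 53 and 54) do have them.
- If they are treated as ungraded, rows for normal and above the upper limit are expected. The second is missing, and the below-LLN bands are not mentioned in 7.7.2.

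On either reading, the post-baseline shells do not follow the text.

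**Which reading is more likely**

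The SAP does not say. The thyroid bullets omit the reference to worst CTC grade that the hematology and chemistry bullets carry. That is weak evidence alone, because the coagulation bullets omit it too and yet have Grade rows. The LLN bands in the shells are the stronger sign that no grade was intended.

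**How other ungraded tests are laid out**
- RBC, monocytes, eosinophils and basophils (Tables 47 and 48), and LDH, chloride and CEA (Tables 49 and 50), have a Normal and a High row. In Tables 47 and 48 the High row carries the footnote "Greater than upper normal limit". That is 7 tests x 2 tables = 14 of 14 blocks.
- The same seven tests have a High row at baseline (Tables 15 and 16): 7 of 7 blocks.
- Thyroid tests: 0 of 10 post-baseline blocks and 0 of 5 baseline blocks.

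The shells also have a pattern for results that can be abnormal in both directions. Tables 49 and 50 give sodium, potassium, calcium, magnesium and albumin separate low and high blocks, for example "Hypermagnesemia".

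**Whether the adverse event tables fill the gap**
- Protocol 9.1.2 keeps abnormalities of protocol-specified tests out of the adverse event record because they are derived from the laboratory values. Its heading limits it to the durvalumab/tremelimumab arm.
- Protocol Appendix III lists asymptomatic TSH elevation under Grade 1 endocrinopathy, so it could be reported as an event.

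These point in opposite directions, so the documents do not settle whether an isolated TSH elevation would reach Tables 42 to 46.

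**The case against.** The strongest reply is that this is a drafting slip, not a gap in the plan. If 7.7.2 governs the thyroid tests, the above-ULN category is already specified and only an unfilled shell lags behind it. Much can still be seen as well: suppressed TSH and low T3 or T4 have rows, and diagnosed thyroid disorders can appear in the adverse event tables. The row counts repeat one template omission, and four of the five tests are required only when TSH is abnormal.

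Most of this stands, and it limits the size of the point. It does not remove it. The remedy would depend on a programmer preferring a general sentence to a specific shell, and the SAP never says that the sentence applies to thyroid tests.

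A reader might infer more than the documents support:
- *That the thyroid shells certainly breach the rule for ungraded tests.* This holds only if the tests are ungraded, which is inferred. The firm statement is that they match neither permitted display.
- *That Table 17 contradicts 7.7.2.* It falls under 7.4.6, which sets no categories. It has a parallel gap only.
- *That the meaning of worst is already a separate fault.* With only Normal and descending low bands, worst is the lowest band. The ambiguity arises once a high row is added, so it is a condition on the fix.
- *That 9.1.2 closes the adverse event route in both arms.* Its heading covers one arm, and Appendix III leaves a possible route.

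**Conclusion.** The point holds as a correction to descriptive safety tables. None of the 40 rows in Tables 51 and 52, and none of the 20 in Table 17, can show a thyroid value above ULN, while every one of the seven other ungraded tests has a High row. The practical loss is narrow: chiefly an isolated TSH elevation, which would be left out or counted as Normal if the shells are followed as drawn.

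The documents give no rate of TSH elevation, so no number of affected patients can be stated. No formal test, efficacy result or sample size is touched. The row counts rest on the shells alone. The specific conflict with the normal-versus-high rule rests on the inference that thyroid tests are ungraded; the mismatch with 7.7.2 as a whole does not.

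**What to change.** - Add one above-ULN row for each thyroid test to Tables 17, 51 and 52: 5 tests x 3 tables = 15 rows.
- In Tables 51 and 52, tabulate low and high abnormalities separately, so that a patient with both appears in each.
- Count a patient as Normal only if all values in that table's own window are within limits. For Table 51 the window is the Treatment Report and the 4-Week Post-Treatment Follow-Up Report; for Table 52 it is all post-baseline values. One rule based on all post-baseline values would wrongly remove from Normal in Table 51 a patient whose only abnormal result came after that window.
- Amend SAP 7.7.2 to say that thyroid tests are summarized as normal, the existing below-LLN bands, and above ULN.

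The cost is shell text, one SAP sentence and programming. No new assessment is needed. This assumes that ULNs are captured along with the LLNs that the shells already require; the case report forms for these results are not in the documents.

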4.3 Safety

The safety endpoints are serious and non-serious adverse events (clinical and laboratory), laboratory parameters, dosing data (including dose interruptions, total delivered dose and dose modifications) and reasons off treatment.

5. Sample Size and Power

The primary objective of this study is to assess the additional effect of durvalumab and tremelimumab to best supportive care by comparing overall survival (OS) between Durva+Treme and BSC arms among all randomized patients. It was calculated that with a 2-sided alpha of 10%, a total of 180 patients with 150 events (deaths) would be required to provide 80% power to detect a 2.4 month difference in median survival (a hazard ratio of 0.65) between the two treatment arms assuming a median survival of 4.5 months for the BSC alone arm. The final analysis will be conducted after at least 150 events have been recorded. It is estimated that 180 patients accrued over 18 months and followed for 6 months will be required to reach the necessary number of events.

6. Data Set Descriptions

Three types of analysis samples will be used:

All Randomized Patients:

All patients who have been randomized in the study with the treatment arm being as randomized.

Response-Evaluable Patients:

All patients who have received at least one cycle of therapy and have their disease re-evaluated will be considered evaluable for response (exceptions will be those who exhibit objective disease progression prior to the end of cycle 1 who will also be considered evaluable).

All Treated Patients:

All patients on Durva+Treme who received at least one dose of durvalumab and tremelimumab and on BSC who had at least one Best Supportive Care Report.

Patients randomized to BSC who have received at least one dose of durvalumab and tremelimumab on study (from Cancer Treatment Section of Best Supportive Care Report) will be grouped with patients randomized to Durva+Treme in analyses of safety.

7. Statistical Analysis

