7.7.1 Adverse Events

Adverse events will be recorded on the CCTG toxicity/adverse event-intercurrent illness case report form. Events reported on Treatment Report or 4-Week Post-Treatment Follow-Up Report for patients on the Durva+Treme arm will be defined as adverse events on Durva+Treme; Events reported on any case report forms except Form 1 will be summarized separately for patients on both arms as overall adverse events during the (whole) study.

Drug related adverse events are those events with a relation to protocol therapy of 3=possible, 4=probable or 5=definite.

Severe adverse events are those events reported with a CTCAE Grade of 3 or higher.

Comparisons between treatment arms on overall adverse events (any vs. other, severe vs. other) will be carried out using a two sided Fisher's exact test at an alpha level of two-sided 10%.

The following variables are summarized. Tabulations of overall adverse events will be presented by treatment group.

- Adverse events on Durva+Treme: worst CTCAE grade per patient (**Table 42**)
- Severe adverse events on Durva+Treme: worst CTCAE grade per patient (**Table 43**)
- Drug related adverse events on Durva+Treme: worst CTCAE grade per patient (**Table 44**)
- Overall adverse events: worst CTCAE grade per patient (**Table 45**)
- Severe overall adverse events: worst CTCAE grade per patient (**Table 46**)

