7.7.4 Deaths on Study/Adverse Events Leading to Discontinuations of Protocol Treatment

- Deaths during durvalumab and tremelimumab treatment or within 4 weeks of last durvalumab and tremelimumab treatment (DURVA+TREME Arm only): number of patients who died and cause of death from Date/Cause of Death Section of Death Report (**Table 57**)
- Number of patients with adverse events leading to discontinuations of durvalumab as identified from Off Protocol Treatment - Adverse Events of End of Treatment Report (DURVA+TREME Arm only) (**Table 58**)
- Number of patients with adverse events leading to discontinuations of tremelimumab as identified from Off Protocol Treatment - Adverse Events of End of Treatment Report (**Table 58**)

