All Durvalumab Administrations According to Protocol	
Yes	** (**)
No	** (**)
All Tremelimumab Administrations According to Protocol	
Yes	** (**)
No	** (**)

Table 27: Dose Reduction, Omission or Delay and IV Rate Decrease and Infusion Interruption for Durvalumab and Tremelimumab

Data Set: All Treated Patients on DURVA+TREME Arm		
	Number of patients (%)	
	Durvalumab (N=***)	Tremelimumab (N=***)
At least one dose reduction	** (**)	** (**)
Reason for dose reduction:		
<reason 1>	** (**)	** (**)
<reason 2>	** (**)	** (**)
...	** (**)	** (**)
At least one dose omission	** (**)	** (**)
Reason for dose omission:		
<reason 1>	** (**)	** (**)
<reason 2>	** (**)	** (**)
...	** (**)	** (**)
At least one dose delay	** (**)	** (**)
Reason for delay:		
<reason 1>	** (**)	** (**)
<reason 2>	** (**)	** (**)
...	** (**)	** (**)
IV rate decrease and infusion interruption	** (**)	** (**)
Reason for decrease and interruption:		
<reason 1>	** (**)	** (**)
<reason 2>	** (**)	** (**)
...	** (**)	** (**)

Table 28: Cumulative Dose of Durvalumab and Tremelimumab

Data Set: All Treated Patients on DURVA+TREME Arm		
	Durvalumab	Tremelimumab
Cumulative dose per patient		
N	***	***
Mean (STD)	** (**)	** (**)
Median	**	**
Min-Max	** _ **	** _ **

Table 29: Dose Intensity of Durvalumab and Tremelimumab

Data Set: All Treated Patients on DURVA+TREME Arm		
	Durvalumab	Tremelimumab
Dose intensity per patient		
N	***	***
Mean (STD)	** (**)	** (**)
Median	**	**
Min-Max	** _ **	** _ **

Table 30: Relative Dose Intensity of Durvalumab and Tremelimumab

Data Set: All Treated Patients on DURVA+TREME Arm		
	Durvalumab	Tremelimumab
Relative Dose intensity		
≥ 90% planned intensity	** (**)	** (**)
≥ 80% - < 90% planned intensity	** (**)	** (**)
≥ 60% - < 80% planned intensity	** (**)	** (**)
< 60% planned intensity	** (**)	** (**)

Table 31: Off Durvalumab and Tremelimumab Treatment Summary

Data set: All Treated Patients on DURVA+TREME Arm		
	Number of patients (%)	
	Durvalumab N=***	Tremelimumab N=***
Patients off Treatment	N = ** (**)	N = ** (**)
Reason off protocol therapy		
Treatment Completed	**	**
Progressive Disease (objective)	**	**
Symptomatic Progression	**	**
Intercurrent Illness – adverse events unrelated to treatment	**	**
Adverse events related to protocol therapy	**	**
Patient Refusal (not related to adverse event)	**	**
Death	**	**
Other Reason	**	**

Table 32: All Deaths

Data set: All Randomized Patients		
	Number of Patients (%)	
	DURVA+TREME N=***	BSC N=***

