	Normal	** (**)	** (**)
	<1-0.5xLLN	** (**)	** (**)
	<0.5-0.1xLLN	** (**)	** (**)
	<0.1xLLN	** (**)	** (**)

Table 53: Coagulation Tests: Worst during Durvalumab and Tremelimumab Treatment

Data set: All Treated Patients on DURVA+TREME		Number of Patients (%)	
		DURVA+TREME N = ***	
PT	Grade 1	** (**)	
	Grade 2	** (**)	
	Grade 3	** (**)	
	Grade 4	** (**)	
INR	Grade 1	** (**)	
	Grade 2	** (**)	
	Grade 3	** (**)	
	Grade 4	** (**)	
PTT	Grade 1	** (**)	
	Grade 2	** (**)	
	Grade 3	** (**)	
	Grade 4	** (**)	

Table 54: Coagulation Tests: Worst during Study

Data set: All Treated Patients		Number of Patients (%)	
		DURVA+TREME N = ***	BSC N = ***
PT	Grade 1	** (**)	** (**)
	Grade 2	** (**)	** (**)
	Grade 3	** (**)	** (**)
	Grade 4	** (**)	** (**)
INR	Grade 1	** (**)	** (**)
	Grade 2	** (**)	** (**)
	Grade 3	** (**)	** (**)
	Grade 4	** (**)	** (**)
PTT	Grade 1	** (**)	** (**)
	Grade 2	** (**)	** (**)
	Grade 3	** (**)	** (**)
	Grade 4	** (**)	** (**)

Table 55: ECG Results

Data set: All Treated Patients		
	Number of patients (%)	
	DURVA+TREME N=***	BSC N=***
ECG reported	*** (**)	*** (**)
All Normal	**	**
At least one abnormal but none clinically important	**	**
At least one abnormal and clinically important		
ECG not reported/not performed	*** (**)	*** (**)

Table 56 : Urinalysis

Data set: All Treated Patients		
	Number of patients (%)	
	ARM A N = **	ARM B N = **
Urinalysis – SPOT Test		
Negative/trace	** (**)	** (**)
1+(>20 mg/dL–30 mg/dL)	** (**)	** (**)
2+(>30 mg/dL–100 mg/dL)	** (**)	** (**)
3+(>100 mg/dL– 300 mg/dL)	** (**)	** (**)
4+(>300 mg/dL)	** (**)	** (**)
Urinalysis – 24-Hour Test (g/day)		
Grade		
1	** (**)	** (**)
2	** (**)	** (**)
3	** (**)	** (**)

Table 57: Deaths During Durvalumab and Tremelimumab Treatment or within 4 weeks of Last Durvalumab and Tremelimumab Treatment

Data set: All Treated Patients on DURVA+TREME Arm	
	Number of Patients (%)
	DURVA+TREME N=***
Number of Patients who died during or within 4 weeks of last Durvalumab and Tremelimumab treatment	** (**)
Cause of Death	
Colorectal cancer	**
Toxicity from protocol treatment	**
Colorectal cancer + Toxicity from protocol treatment complication	**
Non-protocol Treatment Complication	**
Colorectal cancer + Non-protocol Treatment Complication	**
Other Primary Malignancy	**
Other Condition or Circumstance	**

Table 58: Adverse Event leading to Discontinuation of Durvalumab or Tremelimumab^(a)

Data set: All Treated Patients on DURVA+TREME Arm	
	Number of patients (%)
	DURVA+TREME N=***

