Number discontinued durvalumab from adverse events	** (**)
<Adverse event 1>	**
<Adverse event 2>	**
....	
Number discontinued Tremelimumab from adverse events	** (**)
<Adverse event 1>	**
<Adverse event 2>	**
....	

(a) From End of Treatment Form with off reasons= "Adverse events related to protocol therapy".

Table 59: Concomitant Medications

Data set: All Treated Patients		
	Number of patients (%)	
	DURVA+TREME N = ***	BSC N=***
Any concomitant medication during or 4 weeks after Durvalumab and Tremelimumab Treatment for patients on DURVA+TREME and before objective progression on BSC		
No	** (**)	** (**)
Yes	** (**)	** (**)
Type of concomitant medications ⁽¹⁾		
Medication A	** (**)	** (**)
...		

(1): patients may have received more than one concomitant medication.

Table 60: Anti-Cancer Treatment

	Number of patients (%)	
	DURVA+TREME N=***	BSC N=***
Number of patients with any anti-cancer treatment during or 4 weeks after Durvalumab and Tremelimumab Treatment	*** (**)	NAP (NAP)
Chemotherapy ⁽¹⁾	*** (**)	NAP (NAP)
Drug 1 ...	*** (**)	NAP (NAP)
Radiotherapy ⁽¹⁾	*** (**)	NAP (NAP)
Hormonal therapy ⁽¹⁾	*** (**)	NAP (NAP)
Drug 1 ...	*** (**)	NAP (NAP)
Immunotherapy ⁽¹⁾	*** (**)	NAP (NAP)
Drug 1 ...	*** (**)	NAP (NAP)
Other ⁽¹⁾	*** (**)	NAP (NAP)
Drug 1 ...	*** (**)	NAP (NAP)
Number of patients with any anti-cancer treatment before progression	*** (**)	*** (**)
Chemotherapy ⁽¹⁾	*** (**)	*** (**)
Drug 1 ...	*** (**)	*** (**)
Radiotherapy ⁽¹⁾	*** (**)	*** (**)
Hormonal therapy ⁽¹⁾	*** (**)	*** (**)
Drug 1 ...	*** (**)	*** (**)
Immunotherapy ⁽¹⁾	*** (**)	*** (**)
Drug 1 ...	*** (**)	*** (**)
Other ⁽¹⁾	*** (**)	*** (**)
Drug 1 ...	*** (**)	*** (**)
Number of patients with any anti-cancer treatment after progression	*** (**)	*** (**)
Chemotherapy ⁽¹⁾	*** (**)	*** (**)
Drug 1 ...	*** (**)	*** (**)
Radiotherapy ⁽¹⁾	*** (**)	*** (**)
Hormonal therapy ⁽¹⁾	*** (**)	*** (**)
Drug 1 ...	*** (**)	*** (**)
Immunotherapy ⁽¹⁾	*** (**)	*** (**)
Drug 1 ...	*** (**)	*** (**)
Other ⁽¹⁾	*** (**)	*** (**)
Drug 1 ...	*** (**)	*** (**)

(1) Patients could have more than one type of anti-cancer treatment. NA=Not applicable.

Table 61: Major Medical Problems

Data set: All Treated Patients		
	Number of patients (%)	
	DURVA+TREME N = ***	BSC N=***

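### Table 58 is labelled as all adverse events leading to discontinuation but counts only those judged drug-related, and serious adverse events, a named safety endpoint, have no planned table

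*SAP*

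**What the plan says.** **Discontinuation.** SAP 7.7.4 sends to Table 58 the patients with "adverse events leading to discontinuations of durvalumab as identified from Off Protocol Treatment - Adverse Events of End of Treatment Report", and has a matching item for tremelimumab. Table 58 is titled "Adverse Event leading to Discontinuation of Durvalumab or Tremelimumab", and its two row headings give the number who discontinued each drug from adverse events. Neither title nor rows mention relatedness. Footnote (a), attached to the title, restricts the source: "From End of Treatment Form with off reasons" equal to the single category for adverse events related to protocol therapy.

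Table 31, also drawn from the End of Treatment Report, lists the reasons for stopping each drug. It has that related category and, as a separate line, intercurrent illness, explained as "adverse events unrelated to treatment".

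**Seriousness.** SAP 4.3 states: "The safety endpoints are serious and non-serious adverse events (clinical and laboratory" among others. SAP 7.7.1 then defines a different class: "Severe adverse events are those events reported with a CTCAE Grade of 3 or higher". Protocol 9.1 defines a serious event by outcome: death, threat to life, hospitalization, lasting disability or birth defect. It adds that an immune-related event needing high-dose steroids must be reported through the serious-event system. It requires this reporting for Arm 2 but not for best supportive care (BSC).

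**The concern.** Discontinuation for adverse events is one of the first figures a reader looks at to judge tolerability. The trial is open-label (SAP 2.1), and relatedness is judged at the site, in patients whose disease produces many of the same symptoms as the drugs. A table filtered on that judgement, but labelled as if it were not, may be quoted as the all-cause figure.

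The second gap is of a different kind. Serious adverse events are named as an endpoint and collected for Arm 2, but the plan has no output for them. Severe and serious are easily confused, so the grade 3 or higher tables could be mistaken for the missing result.

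**Working it through.** The table shells hold placeholders, so there is no planned figure to reproduce. The check is a comparison of texts, with one line of arithmetic.

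**1. What Table 58 counts.** For one drug, let N be the treated Arm 2 patients, R those whose reason for stopping is a related adverse event, and U those whose reason is an unrelated adverse event.

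- By title and row labels: (R + U)/N
- By footnote (a): R/N
- Shortfall: (R + U)/N − R/N = U/N

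The shortfall is zero only if U = 0. With the 120 patients planned for Arm 2 in SAP 2.1, and assuming all are treated, each omitted patient lowers the figure by 1/120 = 0.0083, or about 0.8 percentage points. Neither document gives a value for R or U.

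**2. What can be recovered.** Table 31 uses the same data set as Table 58 (all treated patients on Arm 2) and shows R and U for each drug. Their sum gives the all-cause count, provided that one reason is recorded per patient and drug. Table 31 does not name the events. Table 58 is the only planned table that links event terms to discontinuation, and it does so for R only.

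**3. How the SAP labels relatedness elsewhere.** Table 44 says in its title that it is limited to drug-related events, and SAP 7.7.1 defines the term. Table 57 reports on-treatment deaths from all causes. Table 58 is labelled like the second and filtered like the first.

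**4. Whether seriousness appears anywhere.**

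| Output | Classified by |
|---|---|
| Tables 42 and 45 | worst grade, any cause |
| Tables 43 and 46 | grade 3 or higher, any cause |
| Table 44 | worst grade, related to either or both drugs |
| Table 57 | deaths on or within 4 weeks of treatment |
| Table 58 | related events leading to discontinuation |

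The rest of SAP 7.7 covers laboratory tests, ECG and urinalysis. Planned tables reporting by seriousness: 0 of 67.

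**5. Whether the severe-event tables could stand in.** They cannot, and the protocol itself supplies a counterexample. Appendix III (General Considerations) describes high-dose intravenous steroids for some events even at grade 2. Under the Protocol 9.1 note, such an event is reportable as serious. It would be absent from Tables 43 and 46, and would appear in Table 42 as an ordinary grade 2 event.

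**The case against.** The strongest reply has five parts.

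- **Arm 2 toxicity as a whole is reported.** A reader might infer from the two gaps that it is under-reported. The documents do not support that: Tables 42, 43, 45 and 46 cover Arm 2 events whatever their attribution, and Table 57 covers on-treatment deaths by cause. Protocol 9.0 has serious events recorded on the case report forms, so they enter the general tables, only without a flag. This stands.
- **The restriction is disclosed and the count is recoverable.** The footnote is on the table, and Table 31 supplies the missing number. This also stands. What remains is a label broader than its content, and event terms that appear nowhere in connection with stopping.
- **SAP 7.7.4 may not contradict the footnote.** A reader might infer a direct conflict. However, 7.7.4 points to a named section of the End of Treatment Report, and that form is not among the documents. If the section holds only related events, the two agree. A conflict is not proven; the mismatch shown is between the footnote and the table's own title and rows.
- **SAP 4.3 may simply mean all adverse events.** Protocol 13.2 promises a summary by type and severity, which Tables 42 to 46 deliver. That reading is possible. But an endpoint that names two classes, with no output separating them, leaves half of its wording without a result.
- **No comparison between arms is possible**, because BSC has no required serious-event reporting. True, but this limits the missing table to Arm 2; it does not make it unnecessary. Nor does the data safety committee's six-monthly review replace a table in the final report.

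**Conclusion.** The point holds as two reporting defects. Table 58, produced as written, gives a discontinuation figure narrower than its label by U/N for each drug, about 0.8 percentage points per omitted patient at N = 120. The serious-event part of a stated endpoint has no output, and the grade-based tables miss lower-grade events that are serious under Protocol 9.1.

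This rests on the Table 31 categories being those of the End of Treatment Report, with one reason per patient and drug. No overall percentage should be attached, since the documents give no rates. The point does not touch the primary analysis, the sample size or any efficacy result. It should be corrected before the report is written, because both figures are likely to be quoted on their own.

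**What to change.** 1. **Table 58.** Change footnote (a) to take both adverse-event reasons, and show total, related and unrelated for each drug, with event terms where the form records them. Whether it records them for intercurrent illness cannot be seen from the documents. At minimum, relabel the title and rows as related events only.
2. **SAP 7.7.4.** Align the two items with whichever version is chosen, stating relatedness explicitly.
3. **New table.** Add one Arm 2 table of patients with at least one serious event reportable under Protocol 9.1 (within 30 days of last treatment, and later if related), by category, all-cause and drug-related. Add a note that BSC has no required serious-event reporting, so the arms cannot be compared. A line for the events of special interest in Protocol 9.1.1 is optional.

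The cost is an edited footnote, a wording change in 7.7.4 and one extra table. The serious-event data are already required from sites. The reported discontinuation figure may become slightly less favourable.
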